7.2. STUDY EVALUATIONS METHODS

7.2.1. Nasal Obstruction Symptom Evaluation (NOSE) Scale

The Nasal Obstruction Symptom Evaluation (NOSE) Scale¹⁸ is a Patient-Reported Outcome (PRO) instrument that will be administered to capture subject perception of the degree of nasal airway patency. The NOSE scale will be completed at the Screening, Baseline, 1 Month, 3 Month, 6 Month, 12 Month, 18 Month and 24 Month visits. The NOSE scale may additionally be completed at the Treatment Visit if more than 1 month from Screening Visit.

The NOSE scale is a validated instrument, which was developed by the American Academy of Otolaryngology—Head and Neck Surgery (AAO-HNS), and has been used in several clinical trials. The scale is brief, easy to complete, and is an important tool for pre- and post-intervention evaluation of symptoms in subjects with nasal obstruction. NOSE Scale allows subjects to quantify their symptoms based on the severity of obstruction.

Subjects will be asked, "Since your last follow up visit, how much of a problem were the following conditions for you?" Specifically, subjects will be asked to rate their perceptions on the Likert scale with respect to the following characteristics:

- Nasal congestion or stuffiness
- Nasal blockage or obstruction
- Trouble breathing through my nose
- Trouble sleeping
- Unable to get enough air through my nose during exercise or exertion

Participants will rate their responses using a Likert scale with response options 0, 1, 2, 3 or 4, as follows:

- (0) Not a Problem
- (1) Very Mild Problem
- (2) Moderate problem
- (3) Fairly Bad Problem
- (4) Severe problem

The responses are rated along the continuum, with a rating of "0 – not a problem" indicating no problem breathing, with a completely free flow of air through the nasal airway; "1 – very mild problem", with only slight obstruction in airflow; "2 – moderate problem", with mouth breathing considered easier; "3 – fairly

Spirox Latera™ implant support of lateral wall cartilage (LATERAL-OR) study	Version 2.0
SPI-CP-301	September 7, 2017

bad problem," with considerable obstruction to airflow; and a rating of "4 – severe problem," with complete blockage and obstruction of the nasal passageway, where the subject cannot breathe through the nose and can only mouth breathe. A copy of the Nasal Obstruction Symptom Evaluation Scale questionnaire is attached (See Addendum B).

7.2.2. NAO Breathing Assessment

A subject's perception of breathing cannot be quantitatively measured, but exists on a continuum from the subject perspective. A Visual Analog Scale (VAS) is a patient-reported outcome instrument that will be used to capture subjects' perception of their ability to breathe through the nose, allowing subjects to indicate the degree of breathing difficulty (or ease) they are currently experiencing. The NAO Breathing Assessment will be completed at the Baseline, 1 Month, 3 Month, 6 Month, 12, 18 Month and 24 Month visits.

Operationally a VAS is a horizontal line, 100mm in length, anchored by word descriptors at each end, as illustrated in **Figure 3**.

The subject will either mark on the line the point that they feel represents their perception of their current state or will communicate the information to the Study Coordinator verbally, who will in turn, mark the form as indicated by the subject. The VAS score is determined by measuring in millimeters from the left end of the line to the point that the patient marks.

Figure 3: Visual Analog Scale. Left side represents 0mm and right side represents 100mm.

7.2.3. Baseline Health Economics Questionnaire

The baseline health economics questionnaire administered during the baseline visit is a PRO used to assess the frequency and type of doctor visits related to the Nasal Airway Obstruction condition over one year prior to procedure.

7.2.4. Post Procedure Health Economics Questionnaire

The post procedure health economics questionnaire administered post-procedure is different from the version completed at baseline in the timeframes being referenced. The post-procedure health economics survey will assess frequency and type of doctor visits related to the Nasal Airway Obstruction condition since the index procedure. Do not include visits related to the study when recording the frequency. Subjects will complete the Questionnaire at the 1 Month, 3 Month, 6 Month and 12 Month visits.

7.2.5. Demographics & Nasal Medical History

Demographic information, such as age, gender, ethnicity, race and date of onset of nasal obstruction will be ascertained at the baseline visit.

Spirox Latera™ implant support of lateral wall cartilage (LATERAL-OR) study	Version 2.0
SPI-CP-301	September 7, 2017

Relevant nasal medical history will also be captured at the baseline visit and will include a complete review of nasal system and evaluation of symptoms, including an assessment of nasal airway obstruction signs and symptoms. A history of prior trauma or surgery, including nasal trauma or surgery, will be noted, as well as other medical conditions. Questions will be asked about the medications used by the subjects, including the types and doses of medications that are used to control nasal obstruction symptoms and the performance of those medications in controlling their symptoms (i.e., OTC medications, nasal sprays, decongestants, nasal airway devices, etc.).

7.2.6. Baseline Nasal Exam

Nasal exams will be conducted during the baseline visit and will include collection of nasal anatomy parameters such as nose length, nose height, width and skin thickness. In addition, each side of the nose will be examined with an endoscope to assess each subject's degree of inferior turbinate hypertrophy and septal deviation (superior and inferior). Each of these will be graded as Normal, Mild, Moderate, or Severe.

7.2.7. Post Procedure Nasal Exam

An internal and external nasal physical exam will be conducted at each follow-up visit to document any changes in nasal appearance. In addition, during 6 months visit, each side of the nose will be examined with an endoscope to assess each subject's remaining degree of inferior turbinate hypertrophy and septal deviation (superior and inferior). Each of these will be graded as Normal, Mild, Moderate, or Severe.

7.2.8. Modified Cottle Maneuver

In order to confirm that the subject has dynamic lateral wall insufficiency (LWI), the Modified Cottle Maneuver should be performed. The assessment will be done at the Screening and Baseline visits.

To test for LWI, the curette, cerumen loop, or similar instrument should be inserted into the nasal cavity and used to gently support the lateral nasal sidewall while the patient is asked to breathe in. The Subject will be asked to verbally report their relative improvement per side using the scale below (See **Figure 4**).

No												Complete
Improvement	0	1	2	3	4	5	6	7	8	9	10	Improvement
8												\odot

Figure 4: Verbally reported improvement in breathing with supported lateral wall.

7.2.9. Lateral Wall Motion Video

Using an endoscope, the investigator will record lateral wall motion at rest and at inspiration for each side of the nasal vestibule. Videos will be collected at the Baseline and 6 Month follow-up Visits. Videos will be transferred to Spirox and will be blinded prior to transfer to independent reviewer. The independent reviewer will make assessment of endoscopic lateral wall insufficiency score (1, 2 or 3).

Spirox will utilize the HIPPA compliant file transfer protocol website (BrickFTP.com) BrickFTP site for the transfer of all images and videos from the site to Spirox for processing and analysis. Each site will only have access to upload and view images in their assigned folder(s) and will not have access to other site's folders on the BrickFTP.

See Addendum C "Lateral Wall Motion Capture Instructions".

Spirox Latera™ implant support of lateral wall cartilage (LATERAL-OR) study	
SPI-CP-301	

7.2.10. Photography - Cosmetic

Review of the nasal appearance changes attributed to the overall procedure as well as those attributed to the Latera Implant will be assessed by an independent physician reviewer.

Photographs will be taken to record baseline nose appearance to evaluate aesthetic changes. Six (6) photographs will be taken at baseline, 3, and 6 month time points four (4) static photographic views (straight, left side, right side and chin-up) will be taken and two (2) at a full inhale photographic views (chin-up view and top-down).

Cosmetic photography review will be limited to approximately 3 sites and subject participation is optional.. Images will be blinded (e.g. black boxes placed over the eyes) by the sponsor prior to being sent to the independent reviewer. Sites selected for cosmetic review will also be sites participating in 3D Photography (see Section 7.2.11). Images will be transferred using BrickFTP site.

See Addendum D "Cosmetic Photo Capture Instructions".

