2.3.2. KNOWN POTENTIAL RISKS

In patients with nasal airway obstruction, three factors may influence a decrease in the cross-sectional area of the nasal passage: (1) deviated septum, (2) enlarged turbinates, and (3) collapsed lateral wall. If all three etiologies are present, the surgeon would offer a treatment that would address all three. Thus, the subjects may undergo Implant placement in conjunction with septoplasty and/or inferior turbinate reduction procedures.

Both septoplasty and turbinectomy procedures are standards of care for the treatment of nasal airway obstruction. In the US alone, there are at least 340,000 of these procedures completed each year. The frequency of peri-operative adverse events is low, with an overall admittance rate of hospitalization of 0.85%. The most common reason for readmissions is hemorrhage¹⁹. Possible risks and complications for each procedure are described below.

Septoplasty procedure risks may include:

- Infections
- Nasal bleeding that may require surgical intervention or nasal packing
- Numbness of the nose, cheeks, and upper lip
- Bruising and swelling of the nose, eyelids, and upper lip
- Scarring, septal perforations, nose shape change including "saddle nose" deformity and nostril asymmetry
- A decreased sense of smell
- General anesthesia effect
- Pain and discomfort in the nose, particularly at the front
- Continued nasal obstruction
- Nasal crusting
- Cerebrospinal fluid leak
- Death

The following complication rates have been reported after septoplasty²⁰:

- Infections 3%
- Hematomas 2-7%
- Septum perforations 3-25%
- Changes in nose shape -5-60%
- Smelling disorders less than 1%

Spirox Latera™ implant support of lateral wall cartilage (LATERAL-OR) study	Version 2.0
SPI-CP-301	September 7, 2017

Turbinate reduction procedure risks may include:

- Mild-to-moderate edema with subsequent nasal obstruction and thick mucus formation
- If mucosal erosion is present, the risk of postoperative bleeding and adherent crust formation increases
- Scar tissue (synechiae) may form between the turbinate and the septum
- Bleeding requiring further intervention
- Empty nose syndrome

The following complication rates have been reported after turbinate reduction:

• Synechiae rates up to 36%²⁰.

Latera[™] implant procedure risks may include:

- Inflammatory foreign body reaction, foreign body sensation, pain or discomfort, infection, and extrusion

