5. STUDY ENROLLMENT AND WITHDRAWAL

5.1. PARTICIPANT INCLUSION CRITERIA

In order to be eligible to participate in this study, an individual must meet all of the following inclusion criteria:

- 1. The subject has NOSE Score \geq 55.
- 2. The subject has dynamic lateral nasal wall insufficiency as confirmed by positive Modified Cottle Maneuver.
- 3. The subject is ≥ 18 years of age.
- 4. The subject is willing and able to provide informed consent and comply with the study protocol.
- 5. The subject is seeking treatment for nasal airway obstruction due to Nasal Valve Collapse (NVC) and is willing to undergo nasal Implant procedure alone or with septoplasty and/or a turbinate reduction procedure in an operating room setting.
- 6. The subject has appropriate nasal and facial anatomy to receive Latera Implant.
- 7. The subject agrees to follow-up examinations through twelve (12) months post operatively.
- 8. The subject has failed to benefit from appropriate maximal medical management [e.g., nasal steroids (at least 4 weeks); antihistamines; oral decongestants; nasal strips, stents, or cones]. Failure of maximal medical management may be from lack of effectiveness or inability of subject to tolerate.

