7.1.3. Treatment Visit (Visit 3)

This visit may be completed in conjunction with Visits 1 and 2, and should take place within 1 month after Visit 1 (Screening & Enrollment Visit). If treatment occurs more than 1 month after Visit 1, inclusion and exclusion criteria must be re-confirmed and the subject will be asked to re-review, initial and date the ICF to continue participation. Subjects will also complete a NOSE scale form.

During this visit, the subject will be treated with the study device according to the Instructions for Use. The procedure will be completed in either a hospital or ASC operating room setting. Only procedure-trained investigators that are authorized by the sponsor will be allowed to place the devices during this study.

The following procedures will be completed for the Index procedure visit and placement of the Latera[™] Implants:

- 1. Subject will receive general anesthesia, monitored anesthesia care (MAC), or conscious sedation per standard operating room procedures.
- 2. Amoxicillin or equivalent antibiotic should be administered via either P.O. or IV to the subject before the Implant(s) is placed.
- 3. Subject will undergo all other planned procedures (e.g., septoplasty and/or turbinate reduction) first, with delivery of the Implant(s) being the last step.
- 4. The skin of the nose and the nasal mucosal surface should be cleaned and prepped with an antiseptic solution (e.g. isopropyl alcohol or betadine ophthalmic).
- 5. The nasal anatomy will be examined and target trajectory for the Implant(s) will be established and marked with the aid of the implant positioning guide per IFU (Addendum A).

- 6. Images of planned placements should be captured.
- 7. Prior to placement of the Implant(s), appropriate topical and local anesthesia should be administered to the injection site, depending upon the physician's judgement; for example a solution of 2% Lidocaine with Epinephrine injected locally (1:100,000) may be used. The anesthesia may be injected along the proposed implantation track, starting at the alar rim and progressing to the supraperiosteal region of the maxilla and along the alar rim at the area of targeted insertion. In addition, an infraorbital nerve block may be administered with the same anesthetic solution.
- 8. The treatment area should also be pre-treated with an antibiotic ointment (e.g. Mupirocin or equivalent) to minimize potential infection risk is recommended.

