10.4.11. EXPLORATORY ANALYSES

Cosmesis changes from baseline to 3 month and 6 months, evaluated by Independent Photo Review at 2 sites only, will also be tabulated.

Version 2.0 eptember 7, 2017

Spirox Latera™ implant support of lateral wall cartilage (LATERAL-OR) study	Version 2.0
SPI-CP-301	September 7, 2017

Endoscopic lateral wall insufficiency score is a 3-level, categorical variable, which will be evaluated for each side separately. Baseline and 6 month post-baseline scores will be cross-tabulated, and the proportion with improvement will be calculated.

Response percentage, change in NOSE scores and other variables including satisfaction will also be evaluated by type of procedure (implant alone versus combinations with septoplasty and/or turbinate reductions).

Resource use will also be summarized.

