APPENDIX II – NONSIGNIFICANT RISK RATIONALE

Background

- The Latera[™] System (Absorbable Nasal Implant and Delivery Device) is a commercially available device that received FDA clearance on June 23, 2016 (K161191). The device is indicated for "supporting nasal upper and lower lateral cartilage." Clinical performance data was submitted in support of the initial Implant clearance (K152958). The Implant and Delivery Device were evaluated in a German clinical study that evaluated device safety and performance in 30 subjects.
- 2. Since clearance was obtained in June 2016, the device has been used in accordance with its cleared indications for use and instructions for use in approximately 300 US commercial cases (with over 500 implants placed, approximately 90% bilateral placement). These cases have included device usage across a spectrum of patients that include both stand alone cases (11%) and cases conducted in conjunction with standard of care procedures (89%) for addressing other types of nasal obstruction (i.e., septoplasty and/or turbinate reduction procedures). To date, no clinically significant complaints or MDR reportable events have been received.
- 3. Spirox developed the subject clinical protocol to evaluate device usage in a controlled manner in the US and to collect data to support potential regulatory applications and publications regarding device usage.
 - a. In the proposed study protocol, the Latera Implant is being used according to its cleared indications for use and instructions for use (i.e., to support nasal lateral cartilage).
 - b. While the Sponsor believes that this study meets the requirements of an exempt study (i.e., device is being used in accordance with its cleared indications for use and instructions for use), Spirox has opted to comply with a higher regulatory standard and as such respectfully requests IRB approval to conduct this study under the abbreviated IDE requirements. The decision to conduct this protocol as an NSR study as opposed to an exempt study affords Spirox with the opportunity to use this data to support potential regulatory applications and publications. For these reasons and those articulated below, Spirox does not believe that device usage under the subject study protocol meets the requirements of a significant risk study.

Non-Significant Risk Rationale for Latera Device

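### In subjects who have septoplasty in the same session, the photo reviewer's implant-attributed appearance reading is confounded and has no stated criteria; tabulate appearance change by procedure type instead

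*Protocol*

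**What the plan says.** Protocol 7.2.10 gives the task to an independent physician and sets it out as follows: "Review of the nasal appearance changes attributed to the overall procedure as well as those attributed to the Latera Implant will be assessed". On timing it says "Six (6) photographs will be taken at baseline, 3, and 6 month time points": four static views and two at full inhalation. On masking it says "Images will be blinded (e.g. black boxes placed over the eyes) by the sponsor". It does not say whether the reviewer knows which procedures the subject had.

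Protocol 7.1.3 fixes the order of surgery: "Subject will undergo all other planned procedures (e.g., septoplasty and/or turbinate reduction) first, with delivery of the Implant(s) being the last step". Section 5.1 also admits subjects who have the implant by itself; the candidate "is willing to undergo nasal Implant procedure alone or with septoplasty and/or a turbinate reduction procedure".

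Protocol 2.3.2 lists complication rates reported after septoplasty, among them "Changes in nose shape -5-60" percent. Its turbinate-reduction risks include no change in outer nose shape.

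Cosmesis change from baseline is an exploratory endpoint in protocol 4.2.3 and SAP 4.5. Neither defines an implant-attributed version. The planned analysis, in protocol 10.4.11, is that cosmesis change, "evaluated by Independent Photo Review at 2 sites only, will also be tabulated". Section 7.2.10 puts the number of cosmetic photo sites at about three and makes subject participation optional.

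**The concern.** The reader is asked to divide one visible change between two causes that acted on the same nose on the same day. For septoplasty, the protocol's own range of 5-60% means the competing cause can be rare or can affect most subjects. If a septoplasty change is assigned to the implant, the implant's cosmetic rate goes up; if an implant change is assigned to septoplasty, it goes down. The photographs of such a subject cannot show which error occurred.

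The stake is a reported figure, not a trial decision. Appendix II says the data may support regulatory applications and publications, and section 2.1 contrasts the implant with surgery that may permanently alter appearance. An implant-attributed cosmetic rate could therefore be cited later, and readers would take it as a measurement.

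**Working it through.** The documents state no sample size, rate or precision for the photo review, so there is no planned figure to reproduce. The check has two parts.

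**1. What the photographs can identify, by procedure type (the four types in SAP 3.4.1)**

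- Implant alone: no concurrent operation. Overall change is change from the implant procedure.
- Implant plus turbinate reduction: protocol 2.3.2 lists no outer shape change for turbinate reduction, and 7.4 describes removing tissue inside the turbinate with the lining left intact. Change is probably interpretable, though the documents do not test this.
- Implant plus septoplasty, with or without turbinate reduction: septoplasty comes first, in the same session. The images captured at the treatment visit are placement-planning images, not cosmetic views. No cosmetic photograph separates the two steps, so the 3 and 6 month images show their sum.

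Size of the competing cause: if the cited 5-60% carried over to these photographs, then per 10 septoplasty subjects 10 × 0.05 = 0.5 to 10 × 0.60 = 6 would show a shape change from septoplasty alone.

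**2. How many subjects would isolate the implant**

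Inputs: at most 170 subjects and about 25 sites (protocol 5.3); 2 or 3 cosmetic sites (10.4.11, 7.2.10). Assumptions: even enrolment across sites and everyone taking part. The trial's procedure mix is not stated. Appendix II gives 11% stand-alone and 89% combined in commercial use, and I use that only as one point in a range.

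Photographed subjects = 170/25 × sites:
- 2 sites: 6.8 × 2 = 13.6, about 14
- 3 sites: 6.8 × 3 = 20.4, about 20

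Implant-alone subjects = that number × assumed share:

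| Implant-alone share | 2 sites | 3 sites |
|---|---|---|
| 11% | 1.5 | 2.2 |
| 25% | 3.4 | 5.1 |
| 50% | 6.8 | 10.2 |

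Chance of no implant-alone subject at an 11% share = (1 − 0.11)^n: 0.89^14 = 0.196 for 2 sites and 0.89^20 = 0.097 for 3 sites.

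Precision when no change is seen: the exact (Clopper-Pearson) two-sided 95% upper limit for 0 of n is 1 − 0.025^(1/n).

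| n | Upper limit |
|---|---|
| 2 | 84% |
| 3 | 71% |
| 5 | 52% |
| 7 | 41% |
| 10 | 31% |

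The 89% is not divided between septoplasty and turbinate-only cases. For each assumed 10 percentage points of turbinate-only subjects, 13.6 × 0.10 = 1.4 to 20.4 × 0.10 = 2.0 more would be probably interpretable. Optional participation lowers every count.

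**The case against.** A reader might infer that the implant-attributed cosmetic result cannot be measured at all. The documents do not support that. Implant-alone subjects are eligible, and nothing concurrent confounds their change. The protocol gives no ground for treating turbinate reduction as a cause of outer shape change. The count of about two unconfounded subjects depends on a commercial case mix that the trial need not follow.

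Nor is it shown that a reader can never separate the two. The implant lies along a marked lateral-wall trajectory, one per side, and the views include both sides, chin-up and inhalation. Section 2.3.2 lists different signs for the two: saddle nose and nostril asymmetry for septoplasty, palpability and skin irritation for the implant. Location therefore carries some information. Physician attribution is also how the protocol handles adverse events (8.2.2). The reviewer's form and the photo-capture addendum are not in the supplied text, so criteria may exist there.

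The strongest point is scale: the endpoint is exploratory, for information only, and tabulated. Protocol 10.4.11 also plans a procedure-type comparison for response, NOSE change and other variables.

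Most of this stands, and it limits the point to septoplasty subjects. It does not remove it. Location is informative only if it is recorded, and neither document asks for that or for any way to check the attribution. The comparison in 10.4.11 does not name cosmesis and pools all combinations. SAP 4.3 splits by procedure type for the primary endpoint only, and SAP 4.5 gives no method for cosmesis.

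**Conclusion.** In subjects who have septoplasty with the implant, the implant-attributed appearance reading is confounded and, on the supplied text, rests on one reviewer's judgement without stated criteria. The conclusion follows from the photograph schedule, the single surgical session and the protocol's 5-60% figure; it does not depend on the assumed case mix.

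Overall appearance change remains interpretable in all photographed subjects. An implant-specific reading remains interpretable in implant-alone subjects and probably in implant-plus-turbinate subjects. No primary or secondary endpoint is touched.

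The unconfounded group is likely to be small: about 2 subjects at an 11% implant-alone share, 3-5 at 25% and 7-10 at 50%, given even enrolment and full participation.

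**What to change.** - Protocol 7.2.10: have the reviewer record whether appearance changed, where on the nose, and in which direction. If attribution to the implant is kept for septoplasty subjects, label it as reviewer judgement.
- Protocol 10.4.11 and SAP 4.5: name cosmesis explicitly and tabulate photo-reviewed change by the four procedure types already listed in SAP 3.4.1, with exact 95% intervals.
- Base any implant-specific cosmetic rate on implant-alone subjects, and show implant plus turbinate reduction separately.
- Separately, reconcile the number of cosmetic photo sites (about 3 in 7.2.10, 2 in 10.4.11).

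The cost is wording on the reviewer form and in the two documents; no new images or visits are needed. The downside is that the implant-specific rate will rest on few subjects and have a wide interval, and the sponsor gives up an unqualified implant-attributed figure for septoplasty subjects.

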4.2.3. EXPLORATORY ENDPOINTS

Exploratory endpoints for informational purposes only:

- 1. Index procedure resource utilization: Anesthesia, procedure time and time to discharge.
- 2. Follow up resource utilization: Nasal airway obstruction related return visits and medication utilization.
- 3. Subject satisfaction questionnaire at 1, 3 and 12 months.
- 4. Degree of nasal way obstruction as reported by subjects on the VAS scale at baseline with decongestant use.
- 5. Endoscopic lateral wall insufficiency score per side²¹ at baseline and 6 months
- 6. 3-D camera lateral wall motion assessment per side at baseline and 3, 6 and 12 months (at select sites).
- 7. Cosmesis changes from baseline evaluated by Independent Photo Review 3 and 6 months (at select sites).
- 8. Allergic rhinitis status at 1, 3, 6 and 12 months.
- 9. Nasal geometry: length of nose, height and width of nose, skin thickness of lateral wall at baseline.
- 10. Type of turbinate procedure.

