7.2.11. Photography – 3D

3D Image capture will be used to evaluate baseline and post-procedure changes regarding the depth and volume of nasal collapse at approximately two sites. 3-D photography review will be limited to approximately 3 sites, and subject participation is optional. Site selection for participation will be based on adequate facility space and staff to support this additional component. Subject participation in 3D photography is optional.

3D Images will be taken to record baseline NVC of both the left and right side of the nose under static conditions and at inhale. Static and inhales images for both sides will be taken at 3, 6 and 12 month time points, to evaluate the change in the nasal collapse depth from baseline.

The Canfield Vectra H1 handheld imaging system allows for the capture and analysis of 3D images. The system is comprised of the Vectra H1 camera, Mirror[®] software and VECTRA Analysis Module. The Vectra H1 camera has an integrated flash to simultaneous capture photographs from dual-angles to build 3-D images. Photographs are either captured to the camera's SD card or tethered to a workstation. Photographs are captured and managed using Canfield Mirror[®] software and is analyzed with Canfield VECTRA Analysis Module. Images will be saved with the camera-generated sequence number (e.g. photo "38"), and then transferred for analysis using the subject ID and study visit for identification. See Addendum D "3D Imaging Procedure" for comprehensive image capture and analysis procedures.

Images will be transferred using BrickFTP site.

See Addendum E "3D Camera Imaging Procedure".

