7.2.14. Discretionary Imaging

In addition to the protocol specific imaging outlined above, the Investigator may wish to share, or Spirox may request, additional images (digital photos) or videos of subject for the purposes of, but not limited to, consultation (e.g. placement of device ahead of procedure, etc.), documentation of changes (e.g. cosmetic change, lateral wall motion, etc.) or adverse event reporting (e.g. image of hematoma). Images may include endoscopic nasal video, digital video or photography. Images or videos may be taken at any time point during the study.

Digital images will be blinded (e.g. black boxes placed over the eyes). Images may be used for educational and/or research purposes. Images or videos will be transferred to Spirox using BrickFTP.

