10.6. MEASURES TO MINIMIZE BIAS

This is a single arm, open label study. Randomization and blinding are not used.

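### The cosmetic photographs are called blinded, but the only masking described hides identity; for neither the photographs nor the lateral wall videos does the protocol say the independent reader is masked to visit.

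*Protocol*

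**What the plan says.** Cosmetic photographs are covered in Protocol 7.2.10. The schedule is "Six (6) photographs will be taken at baseline, 3, and 6 month time points", at approximately 3 sites, with optional participation (10.4.11 says 2 sites). The independent physician reviewer's task is "Review of the nasal appearance changes attributed to the overall procedure as well as those attributed to the Latera Implant". On masking, the section says "Images will be blinded (e.g. black boxes placed over the eyes) by the sponsor prior to being sent to the independent reviewer".

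Endoscopic videos of the lateral wall are covered in 7.2.9. They are recorded for each side at baseline and 6 months, and the independent reviewer gives a score of 1, 2 or 3. On masking: "Videos will be transferred to Spirox and will be blinded prior to transfer to independent reviewer".

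Three other places bear on the meaning. Section 7.2.14, on discretionary imaging, says "Digital images will be blinded (e.g. black boxes placed over the eyes". Section 10.6 says "Randomization and blinding are not used". Section 4.2.3 lists both readings as exploratory, the first as "Cosmesis changes from baseline evaluated by Independent Photo Review 3 and 6 months (at select sites").

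For analysis, Protocol 10.4.11 tabulates the photograph review. It cross-tabulates baseline against 6-month lateral wall scores by side and reports the proportion improved. SAP 4.5 repeats the list of exploratory endpoints and adds nothing on how images are read.

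**The concern.** In a single-arm, open-label study the subjects know they were treated, and NOSE, VAS and satisfaction are all self-reported. Causality of adverse events is judged by the examining clinician (Protocol 8.2.2). A reading by someone outside the treatment adds something different, provided that person does not know which image follows the implant. A reader who does know, and who expects the lateral wall to move less or the appearance to be unchanged, can lean that way in borderline cases without intending to.

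The word used for the images matters too. Appendix II says the data may support regulatory applications and publications. A report that repeats the protocol's term would be understood as masking to time point. If only identity was hidden, that would mislead.

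**Working it through.** No figure in the plan depends on this point, so there is nothing to recompute. The check is a comparison of the relevant text.

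1. **What the example of masking achieves.** A box over the eyes makes a face harder to recognise. It leaves visit, date and image order untouched. The example in 7.2.10 is therefore one of de-identification.

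2. **How the same phrase is used elsewhere.** Section 7.2.14 applies the same term and the same example to discretionary images, which are used for consultation, documentation, education or adverse event reporting. No masked reading is described there, so the natural meaning is removal of identity. This favours the same meaning in 7.2.10, though it does not prove it.

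3. **What is said about time point.** The sections on imaging (7.2.9, 7.2.10, 7.2.14), endpoints (4.2.3), exploratory analysis (10.4.11), bias (10.6) and SAP 4.5 contain no statement that visit or date is stripped, that images are shuffled, or that the reader is unaware of sequence. Section 10.6 disclaims blinding and makes no exception for image readers.

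4. **Whether the reader needs the visit: videos.** Each recording receives its own grade from 1 to 3, and improvement is derived later by cross-tabulation. The grade does not require knowledge of visit, so masking takes nothing away. Each subject contributes 2 visits x 2 sides = 4 side-level grades. At the maximum enrolment of 170 that is at most 170 x 4 = 680 grades.

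5. **Whether the reader needs the visit: photographs.** Each participating subject contributes 3 time points x 6 views = 18 photographs, which form 2 comparisons with baseline (3 and 6 months). Judging whether two sets differ, and in what respect, does not require their order. Attributing a difference to the overall procedure or to the implant may. The two questions can be asked in sequence.

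6. **Reach.** Photographs: 2 to 3 sites, optional, tabulated only. Videos: not limited to select sites in 7.2.9 or in the schedule of events (7.7), summarised as a cross-tabulation and a proportion. Neither reading carries a hypothesis test, and neither enters the primary analysis.

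**The case against.** The strongest reply is that the text is silent rather than wrong. The eye boxes are offered as an example, so a reader might infer that the eyes are the only thing masked, but the wording does not say so. A reader might go further and conclude that the reviewer knows which image is before and which is after. No section says that labels, dates or a fixed order reach the reviewer. Both inferences go beyond the documents. The addenda on motion capture and photograph capture were not available for this review. Their titles concern capture rather than reading, but they could hold more detail.

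The videos are a weaker case still. Section 7.2.9 states outright that they are blinded, and eye boxes cannot be what is meant for an endoscopic view of the nasal vestibule. The fair criticism there is only that the thing hidden is not named.

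The 3D section might seem to settle the matter, because those images are "transferred for analysis using the subject ID and study visit for identification". It does not. That sentence concerns transfer of 3D images for software analysis, with no independent reader described, and says nothing about what the cosmetic reviewer receives.

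Two other inferences also lack support. The documents do not say that one person does both readings, or that the sponsor chose the reader. Nor are these readings the only outcomes free of subject rating: the 3D measurements and the procedure and discharge times are others.

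What survives is narrow. Masking to time point is not stated anywhere in the documents supplied, and the one example given would not achieve it.

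**Conclusion.** The point holds as a gap in specification. Following Protocol 7.2.10 as written yields de-identified photographs, and 7.2.9 does not say that visit is hidden on the videos. The independent reader may therefore be aware of time point, and protection against expectation bias cannot be confirmed for either reading.

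The size of any bias cannot be estimated, because the documents give no expected frequency, agreement rate or target for these endpoints. The consequence is small. The affected results are exploratory and descriptive, and the primary NOSE responder analysis is untouched. This is an inexpensive improvement, not a threat to the trial's main conclusion.

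The conclusion assumes that no addendum or reading charter outside these documents already specifies masking to visit. If one does, a sentence citing it closes the point.

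**What to change.** In Protocol 7.2.9 and 7.2.10, state what is hidden from the independent reader, and have the sponsor do the following before files are sent:

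- Remove visit and date from file names and from any on-screen or embedded label, assign coded labels, and put the files in random order.
- **Videos:** have each recording graded 1 to 3 on its own, without knowledge of visit. The cross-tabulation in 10.4.11 is then built after the key is opened.
- **Photographs:** present each baseline and follow-up pair in random order and have the difference in appearance recorded first. Then open the key and ask for attribution to the overall procedure or the implant. The baseline set belongs to both of a subject's pairs, so keep those two pairs apart in the reading order and open the key only after both are scored.

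If this is not adopted, call the step de-identification in 7.2.10, say the same in 7.2.9 if it applies, and report both readings as not masked to visit.

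The cost is a coding list and a two-step photograph read, with no extra reader. The sponsor already processes the photographs and receives the videos before the reviewer does. One limit remains: relabelling cannot hide a visible sign of surgery within an image, so the report should describe the readings as masked to visit label and order.
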